#### 8.2.2 Immunogenicity

All eligible participants receiving any protocol treatment will be evaluated for the following immune response parameters.

i. Primary:

Circulating CD4+ T cell response to 6MHP peptides where the primary endpoint is the proportion of participants with at least two consecutive 10-fold over baseline responses to the pool of 6MHP peptides.

CD4+ T cell response to 6MHP peptides in the SIN.

ii. Secondary:

Evaluated in the blood and in the SIN

Induction of epitope-spreading for CD8+ T cells reactive to a panel of defined melanoma antigens.

*Evaluated in the tumor microenvironment* (In the subset of participants for which tumor biopsies are obtained pre- and post- treatment) T cell infiltration of CD8+ and/or CD4+FoxP3neg T cells.

iii. Exploratory:

Induction of antibody responses

IgG antibody responses to 6MHP peptides.

#### 8.2.3 Clinical efficacy

All participants receiving any protocol treatment will be evaluated for clinical response to treatment as defined by the following measures.

- i. Exploratory:
  - Overall survival (OS), defined as the time from the date of start of treatment to the date of death from any cause. Participants who do not experience an event (death) will be censored on the date of last follow-up/contact.

# (Cohort 1)

Disease control as assessed by the RECIST 1.1 (CR, PR, SD at 12 weeks) criteria.

Clinical response by irRC criteria.

Progression-free survival (PFS), defined as the time from the date of start of treatment to the date of progression or death from any cause, whichever occurs first. A participant who dies without a reported progression will be considered an event on the date of death. Participants who have neither progressed nor died will be censored on the date of last evaluable tumor assessment.

#### (Cohort 2 and 3)

Disease-free survival (DFS), defined as the time from the date of start of treatment to the date of progression or death from any cause, whichever occurs first. A participant who dies without a reported progression will be considered an event on the date of death. Participants who have neither progressed nor died will be censored on the date of last evaluable tumor assessment.

# 8.3 Sample Size and Accrual

Target sample size is based upon having sufficient information to assess immunogenicity overall cohort conditional on safety bounds not being crossed. Observed immune response from arm D from our most current 6MHP protocol Mel63, provides the basis for sample size determination. Define immune response as 'at least two consecutive 10 fold' responses for 6MHP pool assessed in the blood. Results for Mel63 arm D indicate a immune response rate of 55% (12/22) with 95%CI(32, 76%) satisfy this definition. Accrual of a total of 24 eligible participants provides 80% power to test for a null immune response rate of 55% vs an alternative immune response rate of 80% was chosen to be above the upper limit of the CI to determine that the addition of ipilimumab improved immune response. At study conclusion the null hypothesis will be rejected and the treatment considered worthy of further study if at least 18/24 (75%) eligible participants experience an immune response.

Maximum target sample size is estimated to be 27 participants, which assumes a 10% dropout/ineligibility/lost to follow-up adjustment. Accrual to cohort 3 is expected to accumulate the most participants, at approximately 10 per year, followed by cohort 2 at 3-5 per year, and cohort 1 at 1-3 per year. Therefore, total accrual is estimated at approximately 16 participants per year, therefore, accrual to the study should be completed in less that two years.

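### Reaching 18/24 shows a response rate above a fixed 55%, not that adding ipilimumab improved on the 12/22 seen in Mel63 arm D

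*Combined protocol and SAP*

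**What the plan says.** Section 8.3 (Sample Size and Accrual) gives the source of the null: "Results for Mel63 arm D indicate a immune response rate of 55% (12/22) with 95%CI(32, 76%) satisfy this definition". It then states the power: "Accrual of a total of 24 eligible participants provides 80% power", for 55% against 80%. The 80% alternative "was chosen to be above the upper limit of the CI to determine that the addition of ipilimumab improved immune response". The decision rule follows: "At study conclusion the null hypothesis will be rejected and the treatment considered worthy of further study". The condition attached to that decision reads "if at least 18/24 (75%) eligible participants experience an immune response".

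Two other sections use comparative language. Section 8.1 makes it a primary goal to find out whether anti-CTLA-4 can improve the immune response to the vaccine. Section 8.6 says that 12/15 responders in cohort 3, with a 90% CI of 56% to 94%, would support an improved response rate in that cohort.

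Section 3.3 states that there is no randomization and that all participants receive the same regimen. Nothing in the plan compares the new data with 12/22 in a way that carries the uncertainty of both samples.

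**The concern.** The rule answers one question and the text draws the answer to another. Rejecting a fixed 55% says that the response rate on the combination is above 55%. Saying that ipilimumab improved response is a statement about the difference between vaccine with and without ipilimumab. The only comparator for that difference is 22 people from another study, whose true rate the plan's own interval places anywhere from 32% to 76%.

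If the true vaccine-only rate is somewhat above 55%, the combination can pass without ipilimumab adding anything. At stake is what may be claimed for a primary immunogenicity endpoint when 18 or 19 of 24 respond: the plan would reject the null and its text invites an improvement claim, yet those data are compatible with no difference from the historical arm.

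**Working it through.** **Inputs (section 8.3 unless noted).** Historical arm 12/22; null 55%; alternative 80%; n = 24; success at 18 or more; cohort 3 criterion 12/15 (section 8.6). Alpha and sidedness are not stated.

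**1. The plan's own figures.** With X ~ Binomial(24, p):
- P(X ≥ 18 | p = 0.55) = 0.036 and P(X ≥ 18 | p = 0.80) = 0.811. The stated 80% power reproduces.
- P(X ≥ 17 | p = 0.55) = 0.086, so 18 is the smallest cutoff with one-sided alpha at or below 0.05. A nominal one-sided 5% test is therefore implied.
- The exact (Clopper-Pearson) 95% CI for 12/22 is 32.2% to 75.6%, which matches the printed 32 to 76%.

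**2. Comparison with Mel63 arm D at the threshold.** Newcombe's interval for d = p1 − p2 uses the Wilson limits (l, u) of each proportion: lower = d − √[(p1 − l1)² + (u2 − p2)²], upper = d + √[(u1 − p1)² + (p2 − l2)²].
- Wilson 95% limits: 18/24, 55.1% to 88.0%; 12/22, 34.7% to 73.1%.
- d = 75.0 − 54.5 = 20.5 points.
- Lower = 20.5 − √(19.9² + 18.5²) = 20.5 − 27.2 = −6.7.
- Upper = 20.5 + √(13.0² + 19.9²) = 20.5 + 23.8 = about +44.

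| New data | Difference from 12/22 (points) | 95% CI (Newcombe) | One-sided Fisher p |
|---|---|---|---|
| 18/24 | 20.5 | −7 to +44 | 0.126 |
| 19/24 | 24.6 | −2 to +48 | 0.071 |
| 20/24 | 28.8 | +2 to +51 | 0.035 |
| 12/15 (cohort 3) | 25.5 | −6 to +49 | 0.106 |

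The interval first excludes zero at 20/24. It includes zero at the cohort 3 criterion.

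**3. Chance of passing if ipilimumab adds nothing.** This is P(X ≥ 18 | 24, p) at the true vaccine-only rate p:

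| True vaccine-only rate | Chance of passing |
|---|---|
| 48% | 0.7% |
| 55% | 3.6% |
| 60% | 9.6% |
| 65% | 21.1% |
| 70% | 38.9% |

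All five rates lie inside the plan's 32 to 76% interval.

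**4. Average over the uncertainty in 12/22.** If p follows a beta posterior given 12 responders and 10 non-responders, X is beta-binomial. P(X ≥ 18) is 10.2% with Beta(12, 10), 9.7% with Beta(12.5, 10.5) and 9.2% with Beta(13, 11).

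**The case against.** A fixed historical null is the ordinary single-arm phase II design, and its dependence on the benchmark is a known limitation rather than an error. The arithmetic reproduces, and the formal decision is only that the treatment merits further study. The objectives speak of estimating the response rate, section 1.6 calls the trial a foundation for more definitive work, and section 8.6 already plans 95% CIs. All of this stands, and it is why the rule should stay. But at 18/24 the exact single-sample 95% CI, 53.3% to 90.2%, shows the uncertainty of the new sample only and says nothing about the error in 12/22.

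The higher benchmark rates are hypothetical. Section 1.5 gives blood response rates to the vaccine of 40% (E1602), 48 to 52% (Mel44) and 57% (Mel41), none near 65 to 70%. That is fair, and at 48% the rule is conservative. Adjuvants and co-administered vaccines differed between those trials, however, and the plan itself chose 12/22 as its benchmark. Likewise, the 9 to 10% is a predictive average that depends on a prior; the type I error of the stated test is 3.6%.

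A reader might infer a stronger point: that declaring success at 75% contradicts a requirement to exceed the 76% upper limit. The text does not support this. Section 8.3 says that the 80% alternative was placed above the limit, not that the observed rate must be. A critical value below the alternative is normal, and 75.0% lies below the exact limit of 75.6% by only 0.6 point, where one participant is worth 4.2 points (1/24). Moving the cutoff to 19/24 would cut power at 80% to 66%.

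**Conclusion.** The concern holds as a mismatch between the rule and the claim. The sample size, power and cutoff are correct for a fixed 55%, and 18/24 is a legitimate screen. It does not support the statement in sections 8.1, 8.3 and 8.6 that ipilimumab improved response. At 18/24 the difference from Mel63 arm D is compatible with anything from 7 points worse to 44 points better, and at 12/15 in cohort 3 with 6 points worse to 49 better. With no ipilimumab effect, the chance of passing runs from 0.7% to 21% as the true vaccine-only rate goes from 48% to 65%, and averages 9 to 10% over the uncertainty in 12/22.

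These figures assume independent binomial responses, 24 evaluable participants and a Mel63 arm that is comparable apart from ipilimumab. Section 8.3 gives nothing about arm D beyond its result, so comparability cannot be checked, and the intervals carry sampling error only. Neither a power error nor a contradiction between 75% and 76% is part of this conclusion.

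**What to change.** - Keep n = 24 and the 18/24 rule as the screening decision, and state that it is a one-sided exact test with alpha 3.6% at 55%.
- In sections 8.1, 8.3 and 8.6, replace the improvement wording with: *the response rate exceeds the 55% benchmark and the regimen merits further study*. Changing 8.3 alone would leave the other two sections inconsistent with it.
- Add one supportive analysis: the difference from Mel63 arm D (12/22) with a 95% CI by a method named in advance, such as Newcombe's. The choice matters: at 20/24 Newcombe's interval excludes zero, while the two-sided Fisher p is 0.054.
- Label that analysis as a non-randomised historical comparison. If the interval excludes zero, report that the rate is higher than in the historical arm, not that ipilimumab caused the difference.

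The cost is text in three sections and one extra analysis; sample size, cutoff and participant procedures are unchanged. The claim becomes weaker at 18 or 19 responders. Even at a true rate of 80%, the interval would exclude zero only about 46% of the time, since P(X ≥ 20 | 24, 0.80) = 0.460; the plan should say so.

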# 8.4 Cohort and post entry classification

At study entery participants will be stratified by cohort. In addition. Participants will be monitored for post entry classification by whether or not biopsies are obtained at baseline and one week after the third vaccine; (yes/no). Target sample size for participants for whom biopsies are obtained is set at a minimum of 14 eligible participants. If increased infiltration of CD8+ T cell response from day 1 compared to day 22 tumor is observed in 10/14 participants then the lower limit of a one-sided 90% confidence interval exceeds 50% and would be considered to support further study of the treatment regimen. Similar criteria apply for CD4+FoxP3neg T cells response.

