# Secondary:

Induction of epitope-spreading: To estimate the proportion of patients in whom the combination of 6MHP vaccine plus ipilimumab induces epitope-spreading for CD8+ T cells in the blood and in the sentinel immunized node that are reactive to a panel of defined melanoma antigens.

T cell infiltration of the tumor microenvironment (for cohorts 1 and 2): To determine whether the combination of 6MHP vaccine plus ipilimumab increases infiltration of CD8+ and/or CD4+FoxP3neg T cells into melanoma metastases in at least 50% of patients with tumor evaluable pre- and post-treatment.

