# Biopsies

# Tumor

For participants with metastases safely accessible for biopsy, biopsies will be obtained at baseline and day 22. Such biopsies must be obtained from at least 14 patients in this study. Additional optional biopsies may be performed throughout the study or during follow-up (e.g. at the time of disease progression).

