# Accrual Goal:

To evaluate study endpoints target accrual is estimated at 24 eligible participants, of whom at least 14 must have biopsiable disease. Based upon prior studies, a 10% dropout/ineligibility/lost to follow-up among study participants is possible; therefore maximum accrual to the study is set at 27 participants. The annual accrual rate is projected to be approximately 16 participants; thus, accrual to the study should be completed in less than two years.

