# **3.0 PARTICIPANT SELECTION CRITERIA**

# 3.1 Inclusion Criteria

3.1.1 Participants with stage IIA (with class 2 DecisionDx Score) through IV

melanoma in cohorts defined below. These participants may have had cutaneous, uveal, mucosal primary melanoma, or an unknown primary melanoma. The diagnosis of melanoma must be confirmed by cytological or histological examination. Staging of cutaneous melanoma will be based on the revised AJCC staging system (Appendix 2) (54). Participants must be eligible to be treated with ipilimumab based on clinician judgment within standard of care.

- Cohort 1 (Advanced Patients): unresectable stage III or IV melanoma that have clinical or radiographic evidence of disease.
- Cohort 2 (Neoadjuvant therapy): primary melanoma with clinically apparent lymph node or in transit/satellite lesions with or without lymph node involvement, in transit recurrence or metastatic recurrence amenable to complete resection to no evidence of disease
- Cohort 3 (Adjuvant therapy): Stage IIA (with class 2 DecisionDx Score), IIB-IV melanoma resected to no evidence of disease.
- 3.1.2 Participants will be required to have radiological studies to define radiologically evident disease. Required studies include:
  - Chest CT scan,
  - Abdominal and pelvic CT scan, and
  - Head CT scan or MRI

PET/CT fusion scan may replace scans of the chest, abdomen, and pelvis.

3.1.3 Participants who have melanoma available for biopsy pre-treatment and on day 22 must consent to having those biopsies.

Melanoma lesions may be in nodes, skin, soft tissue, liver, or other sites that can be accessed by core needle biopsy, or incisional or excisional biopsy, with or without image guidance.

The lesion(s) must be large enough to enable biopsy of at least 0.1 cm^3 of tumor tissue (ideally 0.3 cm^3 or more) in 5 core biopsies (ideally 14-16 gauge, but 18 gauge is acceptable) or incisional/excisional biopsies at both time points. Biopsies may be taken from a single lesion or multiple lesions at each of the time points depending on the size of each lesion. Different lesions may be sampled at each time point. It is acceptable to perform a biopsy pretreatment, and then to perform an excision at day 22, even under general anesthesia if needed.

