# Table 8: Stopping Guidelines for DLTs

#### 8.6 Analyses

Study populations and evaluation criteria are noted in Section 8.2. Adverse events will be summarized by frequency and magnitude of event. Incidence of DLTs will be monitored against the safety bounds above. The bounds are non-binding, and provide a guideline that may result in study modification or closure. Participants in cohorts 1 and 2 will be assessed for clinical response and will be classified by disease control by week 12 and at final assessement. DCR will be estimated along with a 95% confidence interval around the point estimate.

Immune response will be measured based upon the methods in Section 7.9. The criteria for defining immune responses have been reported for ELIspot assays (34). The circulating CD4+ T cell response rate to 6MHP peptides in participants treated with 6MHP vaccine plus ipilimumab will be assessed at each time noted in the study calendar. Maximum response over all time periods will be used to estimate the overall CD4+ T cell response. Other measures assessed over time in the blood include epitope-spreading for circulating CD8+ T cells reactive to a panel of defined melanoma antigens, and production of serum IgG reactive to 6MHP. Assessments in the tumor microenvironment include assessment for of CD8+ and/or CD4+FoxP3neg T cells into melanoma. Each participants experiencing an event (immune response, IgG antibody response to 6MHP, presence of CD8+ T cell infiltrates into the tumor (a subset), etc) will be estimated along with 95% confidence intervals. Repeated measure models will be explored to estimate changes over time in interval measurements in the blood and tissue.

Additionally, for cohort 3 only, estimates of immune response within the cohort will be estimated. We expect accrual of at least 15 eligible participants to cohort 3. At study conclusion, if 12/15 (80%) eligible participants satisfy the definition of immune response in cohort 3 then a 90%CI for immune response rate of 80% is (56%, 94%) which would support that immune response rate has improved in that cohort specifically.

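### The required 14 participants with paired tumour biopsies and the 15 or more expected in disease-free cohort 3 total 29, above the 24 eligible and the maximum of 27, and the Section 3.1.3 caps do not fit either total

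*Combined protocol and SAP*

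**What the plan says.** **The biopsy group.** The synopsis, after describing tumour biopsies at baseline and day 22, says: "Such biopsies must be obtained from at least 14 patients in this study". Its accrual goal says: "target accrual is estimated at 24 eligible participants, of whom at least 14 must have biopsiable disease". Section 8.4 repeats the figure: "Target sample size for participants for whom biopsies are obtained is set at a minimum of 14 eligible participants". It defines the group by completed sampling: "Participants will be monitored for post entry classification by whether or not biopsies are obtained at baseline and one week after the third vaccine". If 10 of 14 show increased infiltration, "then the lower limit of a one-sided 90% confidence interval exceeds 50" percent, which would support further study.

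**Cohort 3.** Section 3.1.1 defines it: "Cohort 3 (Adjuvant therapy): Stage IIA (with class 2 DecisionDx Score), IIB-IV melanoma resected to no evidence of disease". Section 8.6 says: "We expect accrual of at least 15 eligible participants to cohort 3". It adds a benchmark of 12/15 with a 90% interval of 56% to 94%. The synopsis restricts the infiltration objective: "T cell infiltration of the tumor microenvironment (for cohorts 1 and 2").

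**Totals and rates.** Section 8.3 sets 24 eligible and a maximum of 27. It projects about 10 per year in cohort 3, 3 to 5 in cohort 2 and 1 to 3 in cohort 1 (about 16 in all), with accrual finished in under two years.

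**Caps.** Section 3.1.3 allows up to 15 participants without biopsiable metastases in a first stage of enrolment and up to 17 in a second. Section 8 has one final test at 24 and a sequential toxicity boundary, and no enrolment stages.

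**The concern.** Two subgroup sizes, each with its own benchmark, look reasonable when read separately. Together they need more participants than the trial will enrol, so at least one benchmark will lack its stated denominator. The plan gives thresholds only for n = 14 and n = 15. A threshold for any other number would have to be chosen later, possibly with the data in view.

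There is also a practical problem during accrual. Whoever registers participants needs one usable limit on those without biopsiable disease. Section 3.1.3 gives two, tied to stages that are not defined, and both are looser than the synopsis implies.

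**Working it through.** **1. The plan's own figures reproduce.**
- Maximum accrual: 24/0.9 = 26.7, rounded up to 27.
- 18/24 rule: exact one-sided error 0.036 at 55%, power 0.811 at 80% (stated 80%).
- 10/14: exact (Clopper-Pearson) one-sided 90% lower limit 0.508. For 9/14 it is 0.437.
- 12/15: exact 90% interval 0.560 to 0.943. For 11/15 the lower limit is 0.489.

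Each figure is sound alone. The problem is how they fit together.

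**2. The groups do not overlap.** Section 6.10 lets qualifying earlier tissue serve as the baseline sample, but Section 8.4 compares it with day 22 tumour. A participant who is disease-free at entry has none to sample.

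**3. The sum.** 14 + 15 = 29, which is 5 above 24 and 2 above 27. Within 24, keeping 14 leaves 24 − 14 = 10 for cohort 3, and keeping 15 leaves 24 − 15 = 9 for biopsies. Within 27 the remainders are 13 and 12.

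**4. Accrual at the Section 8.3 rates**, assuming enrolment is not steered and every cohort 1 or 2 participant yields a pair:

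| Cohorts 1+2 per year | Total per year | Cohorts 1+2 among 24 | Cohort 3 among 24 | Years to reach 14 |
|---|---|---|---|---|
| 4 | 14 | 24 × 4/14 = 6.9 | 17.1 | 14/4 = 3.5 |
| 6 | 16 | 24 × 6/16 = 9.0 | 15.0 | 14/6 = 2.3 |
| 8 | 18 | 24 × 8/18 = 10.7 | 13.3 | 14/8 = 1.75 |

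The middle row matches the 15 in Section 8.6. Reaching 14 within two years needs more than 14/2 = 7 per year from cohorts 1 and 2.

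**5. The caps in Section 3.1.3.** The accrual goal implies that at most 10 of 24 lack biopsiable disease. Against that:
- If cohort 3 counts toward the caps, they leave room for 24 − 15 = 9 or 24 − 17 = 7 biopsiable among 24 eligible. The caps limit enrolment, so the 27 matters too: 27 − 15 = 12 or 27 − 17 = 10. All are below 14.
- If the caps add, 15 + 17 = 32 exceeds 27, so they limit nothing.
- If cohort 3 does not count, the caps do not limit it.

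**6. The benchmarks at other sizes**, using the same exact method:
- Infiltration, one-sided 90% lower limit above 50%: 7/9 (0.510), 8/10 (0.550), 10/14 (0.508).
- Cohort 3, lower limit of the 90% interval above 55%: 9/10 (0.606), 10/12 (0.562), 12/15 (0.560). The 55% is the null of Section 8.3. Section 8.6 does not state it as a criterion; it is inferred from the 56% to 94% interval.

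One fewer success fails in every case.

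**7. Chance of meeting each benchmark (binomial).**
- Cohort 3 at a true 80%, the alternative in Section 8.3: 65% for 12/15, 38% for 9/10.
- Infiltration: the documents give no alternative, so these true rates are assumptions.

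| Assumed true rate | 10/14 | 7/9 |
|---|---|---|
| 60% | 28% | 23% |
| 70% | 58% | 46% |
| 80% | 87% | 74% |

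**The case against.** The strongest reply is that the plan already ranks the two numbers. The 14 is required in three places, and Section 7.7.1 calls the tumour evaluation critical to the protocol. The 15 is only an expectation. The accrual goal already limits those without biopsiable disease to 10 of 24, and Section 8.4 stratifies by cohort and monitors biopsy status. On that reading the team steers enrolment, cohort 3 falls to 10 or fewer, and the requirement is met. At the top of the projected rates, 14 takes 1.75 years. The caps are ceilings and do not force those counts.

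Much of this stands. A reader might infer from the accrual rates that the 14 is the mistaken figure. The documents do not support that: only projected rates point that way, while the wording favours the 14. A reader might also infer that Section 3.1.3 is the only control on enrolment, or that the 14 cannot be reached. Neither holds, because the accrual goal is itself a composition rule and enrolment can be steered toward it.

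The reply does not remove the inconsistency. If the 14 is kept, Section 8.6 still expects 15 and sets a benchmark on 15, Section 8.3 still projects accrual that yields about 9 in cohorts 1 and 2, and Section 3.1.3 still admits more participants without biopsiable disease than the accrual goal allows.

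**Conclusion.** The concern holds as an inconsistency among stated sizes. The required 14 and the expected 15 or more cannot both be reached within 24 or 27, and the 10/14 and 12/15 benchmarks cannot both be used as written. The caps in Section 3.1.3 refer to undefined stages and, on every reading, fail to secure the 14.

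The sum of 29 rests only on the documents. The figure of about 9 of 24 (7 to 11) also assumes that enrolment is not steered and that every cohort 1 or 2 participant yields a pair.

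The reach is limited. A reader might infer that the primary conclusion or the safety monitoring is compromised. It is not: the 18/24 rule and the toxicity boundary do not depend on the cohort mix. Infiltration is secondary in the synopsis and Section 8.2.2 and exploratory in Section 2.3, and the cohort 3 rate is supplementary. Both can be estimated with confidence intervals at any number. It should be fixed, because enrolment needs a workable cap and the thresholds should be set before the data are seen.

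**What to change.** In Section 3.1.3, delete the stage wording and the caps of 15 and 17. Put in one cap consistent with the accrual goal and with 24/27, and say whether cohort 3 counts toward it. Reconcile Sections 3.1.3, 8.3, 8.4, 8.6 and the synopsis.

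- **Following the plan's own wording:** keep the minimum of 14, allow no more than 10 of 24 without biopsiable disease (cohort 3 included), restate expected cohort 3 accrual as about 10 or fewer, and update the accrual time.
- **If the sponsor prefers about 15 in cohort 3:** restate the biopsy minimum as an expected count of about 9. This relaxes a requirement stated three times, so it should be a deliberate choice.

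In either case, say whether the 14 counts participants with biopsiable disease (accrual goal) or completed pairs (Section 8.4); a cap on enrolment secures only the former. Write both benchmarks as criteria applied at the observed number: for infiltration, an exact one-sided 90% lower limit above 50%; for cohort 3, an exact 90% interval with lower limit above 55%. The counts in step 6 can serve as examples.

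The change is to protocol wording and adds no participants. The cost is precision in the reduced group. Keeping the 14 lowers the chance of meeting the cohort 3 benchmark from 65% to 38% at a true 80% (12/15 against 9/10) and takes accrual past two years unless cohorts 1 and 2 exceed 7 per year. Keeping about 15 in cohort 3 lowers the infiltration chance by about 5 to 13 percentage points over the assumed rates in step 7.
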